14.2 Protocol Deviations

The investigator should not deviate from the protocol, except where necessary to eliminate an immediate hazard to study subjects. Should other unexpected circumstances arise that will require deviation from protocol-specified procedures, the investigator should consult with the sponsor or designee (and IRB, as required) to determine the appropriate course of action. There will be no exemptions (a prospectively approved deviation) from the inclusion or exclusion criteria.

The site should document all protocol deviations in the subject's source documents. In the event of a significant deviation, the site should notify the sponsor or its designee (and IRB, as required). Significant deviations include, but are not limited to, those that involve fraud or misconduct, increase the health risk to the subject, or confound interpretation of primary study assessment. A Protocol Deviation Form should be completed by the site and signed by the sponsor or its designee for any significant deviation from the protocol.

14.3 Quality Assurance Audits and Regulatory Agency Inspections

The study site also may be subject to quality assurance audits by the sponsor or its designees. In this circumstance, the sponsor-designated auditor will contact the site in advance to arrange an auditing visit. The auditor may ask to visit the facilities where laboratory samples are collected or where the study drug is stored and prepared, and any other facility used during the study. In addition, there is the possibility that this study may be inspected by the US regulatory agency, the FDA. If the study site is contacted for an inspection by the FDA, the sponsor should be notified immediately. The investigator and study site guarantee access for quality assurance auditors to all study documents as described in Section 14.1.

15.0 ETHICAL ASPECTS OF THE STUDY

This study will be conducted with the highest respect for the individual participants (ie, subjects) according to the protocol, the ethical principles that have their origin in the Declaration of Helsinki, and the ICH Harmonised Tripartite Guideline for GCP. Each investigator will conduct the study according to applicable local or regional regulatory requirements and align his or her conduct in accordance with the “Responsibilities of the Investigator” that are listed in [Appendix B](#). The principles of Helsinki are addressed through the protocol and through appendices containing requirements for informed consent and investigator responsibilities.

15.1 Institutional Review Board Approval

IRBs must be constituted according to the applicable state and federal requirements of each participating region. The sponsor or its designee will require documentation noting all names and titles of members who make up the respective IRB. If any member of the IRB has direct participation in this study, written notification regarding his or her abstinence from voting must also be obtained. Those Americas sites unwilling to provide names and titles of all members due to privacy and conflict of interest concerns should instead provide a Federal Wide Assurance Number or comparable number assigned by the Department of Health and Human Services.

The sponsor or its designee will supply relevant documents for submission to the respective IRB for the protocol's review and approval. This protocol, the Investigator's Brochure, a copy of the informed consent form, and, if applicable, subject recruitment materials and/or advertisements and other documents required by all applicable laws and regulations, must be submitted to a central or local IRB for approval. The IRB's written approval of the protocol and subject informed consent must be obtained and submitted to the sponsor or its designee before commencement of the study (ie, before shipment of the sponsor-supplied drug or study-specific screening activity). The IRB approval must refer to the study by exact protocol title, number, and version date; identify versions of other documents (eg, informed consent form) reviewed; and state the approval date. The sponsor will notify the site once the sponsor has confirmed the adequacy of site regulatory documentation and, when applicable, the sponsor has received permission from competent authority to begin the study. Until the site receives notification, no protocol activities, including screening may occur.

Study sites must adhere to all requirements stipulated by their respective IRB. This may include notification to the IRB regarding protocol amendments, updates to the informed consent form, recruitment materials intended for viewing by subjects, local safety reporting requirements, reports and updates regarding the ongoing review of the study at intervals specified by the respective IRB, and submission of the investigator's final status report to IRB. All IRB approvals and relevant documentation for these items must be provided to the sponsor or its designee.

Subject incentives should not exert undue influence for participation. Payments to subjects must be approved by the IRB and sponsor.

15.2 Subject Information, Informed Consent, and Subject Authorization

Written consent documents will embody the elements of informed consent as described in the Declaration of Helsinki and the ICH Guidelines for GCP and will be in accordance with all applicable laws and regulations. The informed consent form, subject authorization form (if applicable), and subject information sheet (if applicable) describe the planned and permitted uses, transfers, and disclosures of the subject's personal and personal health information for purposes of conducting the study. The informed consent form and the subject information sheet (if applicable) further explain the nature of the study, its objectives, and potential risks and benefits, as well as the date informed consent is given. The informed consent form will detail the requirements of the participant and the fact that he or she is free to withdraw at any time without giving a reason and without prejudice to his or her further medical care.

The investigator is responsible for the preparation, content, and IRB approval of the informed consent form and if applicable, the subject authorization form. The informed consent form, subject authorization form (if applicable), and subject information sheet (if applicable) must be approved by both the IRB and the sponsor prior to use.

The informed consent form, subject authorization form (if applicable), and subject information sheet (if applicable) must be written in a language fully comprehensible to the prospective subject. It is the responsibility of the investigator to explain the detailed elements of the informed consent form, subject authorization form (if applicable), and subject information sheet (if applicable) to the subject. Information should be given in both oral and written form whenever possible and in the manner deemed appropriate by the IRB.

The subject must be given ample opportunity to: (1) inquire about details of the study and (2) decide whether or not to participate in the study. If the subject determines he or she will participate in the study, then the informed consent form and subject authorization form (if applicable) must be signed and dated by the subject at the time of consent and prior to the subject entering into the study. The subject should be instructed to sign using their legal names, not nicknames, using blue or black ballpoint ink. The investigator must also sign and date the informed consent form and subject authorization (if applicable) at the time of consent and prior to subject entering into the study; however, the sponsor may allow a designee of the investigator to sign to the extent permitted by applicable law.

Once signed, the original informed consent form, subject authorization form (if applicable), and subject information sheet (if applicable) will be stored in the investigator's site file. The investigator must document the date the subject signs the informed consent in the subject's medical record. Copies of the signed informed consent form, the signed subject authorization form (if applicable), and subject information sheet (if applicable) shall be given to the subject.

All revised informed consent forms must be reviewed and signed by relevant subjects in the same manner as the original informed consent. The date the revised consent was obtained should be recorded in the subject's medical record, and the subject should receive a copy of the revised informed consent form.

Subjects who consented and provided PGx samples for DNA and RNA analysis can withdraw their consent and request disposal of a stored sample at any time prior to analysis. Notify sponsor of consent withdrawal.

15.3 Subject Confidentiality

The sponsor and designees affirm and uphold the principle of the subject's right to protection against invasion of privacy. Throughout this study, a subject's source data will only be linked to the sponsor's clinical study database or documentation via a subject ID number. As permitted by all applicable laws and regulations, limited subject attributes, such as sex, age, or date of birth, and subject initials may be used to verify the subject and accuracy of the subject's unique ID number.

To comply with ICH Guidelines for GCP and to verify compliance with this protocol, the sponsor requires the investigator to permit the monitor or the sponsor's designee, representatives from any regulatory authority (eg, FDA, Medicines and Healthcare products Regulatory Agency, Pharmaceuticals and Medical Devices Agency), the sponsor's designated auditors, and the appropriate IRBs to review the subject's original medical records (source data or documents), including, but not limited to, laboratory test result reports, ECG reports, admission and discharge summaries for hospital admissions occurring during a subject's study participation, and autopsy reports. Access to a subject's original medical records requires the specific authorization of the subject as part of the informed consent process (see Section 15.2).

Copies of any subject source documents that are provided to the sponsor must have certain personally identifiable information removed (ie, subject name, address, and other identifier fields not collected on the subject's eCRF).

15.4 Publication, Disclosure, and Clinical Trial Registration Policy

15.4.1 Publication and Disclosure

The investigator is obliged to provide the sponsor with complete test results and all data derived by the investigator from the study. During and after the study, only the sponsor may make study information available to other study investigators or to regulatory agencies, except as required by law or regulation. Except as otherwise allowable in the study site agreement, any public disclosure (including publicly accessible websites) related to the protocol or study results, other than study recruitment materials and/or advertisements, is the sole responsibility of the sponsor.

The sponsor may publish any data and information from the study (including data and information generated by the investigator) without the consent of the investigator. Manuscript authorship for any peer-reviewed publication will appropriately reflect contributions to the production and review of the document. All publications and presentations must be prepared in accordance with this section and the study site agreement. In the event of any discrepancy between the protocol and the study site agreement, the study site agreement will prevail.

15.4.2 Clinical Trial Registration

In order to ensure that information on clinical trials reaches the public in a timely manner and to comply with applicable laws, regulations, and guidance, Takeda will, at a minimum, register all interventional clinical trials it sponsors anywhere in the world on ClinicalTrials.gov and/or other publicly accessible websites before start of study, as defined in Takeda Policy/Standard. Takeda contact information, along with investigator's city, state (for Americas investigators), country, and recruiting status will be registered and available for public viewing.

For some registries, Takeda will assist callers in locating study sites closest to their homes by providing the investigator name, address, and phone number to the callers requesting trial information. Once subjects receive investigator contact information, they may call the site requesting enrollment into the trial. The investigative sites are encouraged to handle the trial inquiries according to their established subject screening process. If the caller asks additional questions beyond the topic of trial enrollment, they should be referred to the sponsor.

Any investigator who objects to the sponsor providing this information to callers must provide the sponsor with a written notice requesting that their information not be listed on the registry site.

15.4.3 Clinical Trial Results Disclosure

Takeda will post the results of clinical trials on ClinicalTrials.gov and/or other publicly accessible websites, as required by Takeda Policy/Standard, applicable laws and/or regulations.

15.5 Insurance and Compensation for Injury

Each subject in the study must be insured in accordance with the regulations applicable to the site where the subject is participating. If a local underwriter is required, then the sponsor or sponsor's designee will obtain clinical study insurance against the risk of injury to study subjects. Refer to the study site agreement regarding the sponsor's policy on subject compensation and treatment for injury. If the investigator has questions regarding this policy, he or she should contact the sponsor or sponsor's designee.

Appendix A Schedule of Study Procedures

Study Day/Week:	Screening Period	Base-line	Double-Blind Treatment Period				Final Visit/ET Visit (a)	Follow-up Contact (b)
	Days -28 to -1	Day 0	Week 1	Week 2	Week 3	Week 4	Week 5	Week 7
Visit Windows (Days Relative to Baseline [Day 0]):		0	±3	±3	±3	±3	±3	±5
Visit Number:	1	2	3	4	5	6	7	
Screening/Baseline Procedures								
Informed consent	X							
Subject registry database	X							
Demographics, medical and/or psychiatric history, medication history	X							
Height, BMI	X							
ECG	X							
HBsAg, HCV, HIV, free testosterone, TSH, free T4, HbA1c (c)	X							
Urine drug screen	X	X						
Concurrent medical and psychiatric conditions	X	X (d)						
Inclusion/exclusion criteria	X	X (d)						
Eligibility verification	X	X (e)						
Safety Assessments								
Physical examination, weight	X	X					X	
Vital signs	X	X		X			X	
Concomitant medications	X	X	X	X	X	X	X	X
Hematology, serum chemistry, urinalysis	X	X (f)					X (f)	
C-SSRS	X	X	X	X	X	X	X	
PTE assessment (g)	X	X						
AE assessments (h)			X	X	X	X	X	X
Pregnancy test (hCG) (i)	X	X	X	X	X	X	X	
Sexual Functioning Assessments								
CSFQ-14 (j)	X	X	X	X	X	X	X	
PGI-I (j)			X	X	X	X	X	
Other Blood Sampling								
PK sample collection (k)					X	X	X	
DNA PGx sample collection (l)		X						
RNA PGx sample collection (m)		X					X	
Clinical Supplies								
Contact IWRS for subject ID/medication ID/subject status	X	X	X	X	X	X	X	

CONFIDENTIAL

Study Day/Week:	Screening Period	Base-line	Double-Blind Treatment Period					Final Visit/ET Visit (a)	Follow-up Contact (b)
	Days -28 to -1	Day 0	Week 1	Week 2	Week 3	Week 4	Week 5	Week 7	
Study drug compliance technology		X	X	X	X	X	X		
Dispense study drug		X (n)	X	X	X	X			
Study drug return/accountability/compliance			X	X	X	X	X		

(a) Final Visit procedures to be conducted for subjects who withdraw early, except for those who withdraw their consent and refuse further contact.

(b) The Follow-up Contact will be conducted by telephone.

(c) TSH to be measured at Screening to exclude subjects with clinically significant thyroid dysfunction (hyperthyroidism or hypothyroidism), which may impact sexual functioning. If TSH value is outside the normal range, free T4 will be measured.

(d) To be updated at Baseline.

(e) A prerandomization form must be approved by the PPD medical monitor prior to randomization.

(f) Blood samples for clinical laboratory tests to be collected under fasting conditions at Baseline and Week 5/ET.

(g) PTEs to be assessed from the date of Screening up to the first dose of study drug on Day 1.

(h) AEs to be assessed daily from the first dose of study drug on Day 1 until the Follow-up Contact at Week 7.

(i) Serum test at Screening and urine test at all other visits. For women of child-bearing potential only.

(j) The subject should complete the CSFQ-14 before the PGI-I.

(k) Six PK blood samples to be collected for each subject (2 samples at each time point at Weeks 3, 4, and 5/ET) for measurement of plasma vortioxetine or paroxetine concentrations. At Week 5/ET, the blood sample will be collected at the same time point as the blood sample for clinical laboratory tests. Subjects will be instructed to take the study drug immediately after collection of the PK blood sample.

(l) One 6-mL whole blood sample to be collected for DNA isolation predose at Baseline (Day 0) from each subject.

(m) Two 2.5-mL whole blood samples to be collected for RNA isolation predose at Baseline (Day 0) and also at Week 5/ET from each subject (ie, 4 samples per subject).

(n) Subjects are to be instructed to take the first dose of study drug on the morning of Day 1 (morning after Baseline).

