7.1.3 Definition of Study Day and Study Visit Windows

A windowing convention will be used to determine the analysis value for a given study visit that applies to observed data.

Study Day -1 corresponds to the date of the Baseline visit, ie, the randomization date. Other study days are defined relative to Study Day 1, the date of first double-blind study drug dose. Relative day is calculated as (date of interest – date of first dose +1) for study days on or after the

date of first dose and as (date of interest – date of first dose) for study days prior to the first dose date.

For each visit, a window will be defined such that the lower and upper bounds of each window is generally the midpoint between 2 consecutive study visits. The visit windows and applicable study day ranges are presented below in [Table 7.a](#).

Table 7.a Visit Windows

Nominal Visit Week	Nominal Visit Day	CSFQ-14, PGI-I, C-SSRS	Vital signs	Lab, PE,Weight,	PK
Baseline	-1 (a)	≤1 (b)	≤1	≤1	≤1 (b)
1	7	2 – 10			
2	14	11 – 17	2-24		
3	21	18 – 24			2-24
4	28	25 – 31			25-31
5	35	≥32	≥25	≥2	≥32
7	49				

(a) Baseline day has been defined as Day -1 in keeping with Clinical Data Interchange Consortium standards. There is no Day 0.

(b) No baseline assessment for PGI-I or pharmacokinetic (PK) sampling.

More than 1 result for a parameter may be obtained in a visit window. In such an event, the result with the date closest to the scheduled visit day will be used. In the event of 2 observations equidistant to the scheduled visit day, the later of the observations will be used. Treatment Period Last Visit values will be defined irrespective of falling in a particular window. Hence, the windowed Week 8 value may be different than the Last Visit value.

In general, the baseline value for a variable is defined as the last observation prior to the first dose of double-blind study medication (visit date \leq first dose date), including the screening value, if necessary.

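### The visit schedule counts from Baseline but the SAP's analysis windows count from first dose, so a late starter's Week 5 CSFQ-14 score taken early in its permitted window can be discarded or relabelled Week 4 (minor)

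*Protocol*

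**What the plan says.** The schedule in Protocol Appendix A, reprinted as SAP Appendix A, gives visit tolerances in a row that begins "Visit Windows (Days Relative to Baseline [Day 0". The tolerance is ±3 days at Weeks 1 to 5.

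SAP 7.1.3 uses a different origin: "Other study days are defined relative to Study Day 1, the date of first double-blind study drug dose". The relative day is "date of interest – date of first dose +1) for study days on or after" the first-dose date. The section also states that "Study Day -1 corresponds to the date of the Baseline visit, ie, the randomization date". In SAP Table 7.a the CSFQ-14 windows are days 2–10, 11–17, 18–24, 25–31 and 32 or later, for nominal days 7, 14, 21, 28 and 35. Each bound is "generally the midpoint between 2 consecutive study visits". If two results share a window, "In such an event, the result with the date closest to the scheduled visit day will be used", and a tie goes to the later one.

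The footnotes to Appendix A link the two origins: "Subjects are to be instructed to take the first dose of study drug on the morning of Day 1 (morning after Baseline"). This is an instruction to the subject. SAP 7.1.3 supplies a substitute first-dose date when that date is missing. Neither document has a windowing rule for a known late start.

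SAP 7.1.3 also says that "Treatment Period Last Visit values will be defined irrespective of falling in a particular window". SAP 7.9.2 fills a missing post-baseline assessment with the previous observed value. SAP 7.9.3 specifies LOCF for the primary ANCOVA but does not say whether the Week 5 value comes from windowed visits or from the Last Visit value.

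**The concern.** The last permitted Week 4 day and the first permitted Week 5 day sit exactly on the SAP's boundary between days 31 and 32. With no slack there, moving the origin by one day moves a permitted Week 5 visit into the Week 4 window.

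A short delay need not mark the subject as non-compliant. The per-protocol exclusion in SAP 7.2 requires compliance below 70% or 4 consecutive missed days. SAP 7.8 divides capsules taken by the days from first to last dose, so days before the first dose are never counted. A completer who starts one to three days late can therefore pass every compliance rule, attend inside the permitted window, and still have no windowed Week 5 score.

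At stake are the Week 5 data in the observed-case ANCOVA and the MMRM and, on one reading of the LOCF rule, the value used in the primary analysis.

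**Working it through.** **Inputs.** Permitted days after Baseline: Week 4 is 28 ± 3 = 25–31 and Week 5 is 35 ± 3 = 32–38 (Appendix A). The windows, day formula and selection rule are from SAP 7.1.3.

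**Reproducing Table 7.a.** Midpoints of the nominal days 7, 14, 21, 28, 35 are 10.5, 17.5, 24.5 and 31.5. These give 2–10, 11–17, 18–24, 25–31 and ≥32, exactly as stated.

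**Linking the scales.** Let D be days after Baseline and k the number of days by which the first dose is later than Baseline + 1. First dose = Baseline + 1 + k, so

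SAP day = D − (1 + k) + 1 = D − k.

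- k = 0: D = 32–38 maps to SAP days 32–38. All seven permitted days are Week 5, so there is no problem.
- k = 1: D = 32 maps to day 31 (Week 4), so one of seven permitted days is affected.
- k = 2: D = 32–33 are affected.
- k = 3: D = 32–34 are affected.
- The nominal Week 5 visit (D = 35) maps to day 31 only from k = 4.

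The same shift applies at the lower edges of Weeks 2, 3 and 4. At k = 1, visits on D = 11, 18 and 25 move to the preceding window.

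**What happens to the displaced score.** Take k = 1 with the Week 5 visit on D = 32 (SAP day 31, 3 days from nominal day 28):

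- Week 4 visit on D = 25: SAP day 24, in the Week 3 window. The Week 5 score is the only result in Week 4 and is relabelled.
- Week 4 visit on D = 26: SAP day 25, also 3 days from nominal. The tie goes to the later result, so the Week 5 score is relabelled.
- Week 4 visit on D = 27–31: SAP days 26–30, closer to day 28. The Week 5 score is discarded.

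Repeating this over all 7 × 7 = 49 pairs of permitted Week 4 and Week 5 days:

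| k | Windowed Week 5 missing | Discarded | Relabelled Week 4 |
|---|---|---|---|
| 1 | 7/49 (14%) | 5 (10%) | 2 |
| 2 | 14/49 (29%) | 7 (14%) | 7 |
| 3 | 21/49 (43%) | 6 (12%) | 15 |

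The percentages treat every permitted day as equally likely, which is an assumption.

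**Effect by analysis.** In the observed-case ANCOVA and the MMRM, Week 5 is missing for every pair in the second column. With LOCF built from windowed visits, a relabelled score is carried forward to Week 5 as the same number. Only a discarded score is replaced, by the Week 4 score. For k = 1 to 3, that Week 4 score was always taken 1 to 5 days earlier. With LOCF built from the Last Visit value, the primary value does not change.

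**Illustrative size.** The share of late starters is not given. Suppose 2% to 10% of 352 subjects (7.04 to 35.2) start late, all by the same k:

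- Windowed Week 5 missing: k = 1, × 7/49 = 1.0 to 5.0 subjects; k = 2, × 14/49 = 2.0 to 10.1.
- Primary LOCF value changed, on the windowed reading: k = 1, × 5/49 = 0.7 to 3.6; k = 2, × 7/49 = 1.0 to 5.0; k = 3, × 6/49 = 0.9 to 4.3.

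These counts are across all four arms.

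**The case against.** The strongest reply is that nothing goes wrong if the plan is followed. Dosing on the day after Baseline is specified repeatedly, and the two scales then coincide. The compliance application in Protocol 9.2 reminds the subject and alerts the site to a dose not taken, so late starts should be few. This stands: the effect depends on a departure from the dosing instruction whose frequency is unknown.

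A second reply is that counting from first dose is reasonable in itself, since the endpoint is defined after 5 weeks of treatment, and a site's scheduling tolerance need not share an origin with an analysis window. It is indeed a legitimate choice. It does not justify identical edges on two origins with no rule for when they separate. The Day -1 label for Baseline is inexact for a late starter but harmless, because the Baseline window (day 1 or earlier) still captures the assessment.

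Third, a reader might infer that 14%, 29% or 43% of late starters would have a wrong primary value. The documents do not support that. Those figures include relabelled scores, which LOCF returns to Week 5 unchanged, and the primary analysis is untouched if it uses the Last Visit value. Nor does a one-day delay lose an on-time visit in the ordinary sense: only a visit on the earliest permitted day is affected. If visits cluster near their nominal days, such edge visits are rarer than 1 in 7.

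Finally, no bias is shown. A delayed first dose precedes any drug effect in a randomised, blinded trial. Suppose, as an assumption, that 5 subjects in one 88-subject arm each shifted by 2 points. That arm's mean would move by 5 × 2 / 88 = 0.11, against a design difference of 4.0. This also stands.

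**Conclusion.** The inconsistency is real but minor. Two origins with identical edges let a stated rule remove a valid, in-window Week 5 score from the observed-case ANCOVA and the MMRM for a subject the plan otherwise treats as compliant. Both analyses are supportive, not primary.

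For the primary analysis the risk is conditional. It needs a late start, a Week 5 visit on one of the earliest k permitted days, a Week 4 score closer to day 28, and LOCF built from windowed visits. SAP 7.9.3 leaves the last condition open. SAP 7.1.3 itself warns that the windowed final value and the Last Visit value can differ, and does so for a Week 8 that this study does not have.

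The size is zero with no late starters and probably a handful of subjects at most. That judgement rests on the assumed late-start range and uniform visit days. The documents do not support a claim that the primary result would be biased or materially altered.

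**What to change.** Amend SAP 7.1.3 before unblinding:

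- Assign any scheduled CSFQ-14 visit inside its Appendix A window to its nominal week, and give it precedence over other results in that week. Alternatively, compute the windowing day as visit date minus Baseline date. Either way, all seven permitted Week 5 days map to Week 5.
- Under the first option, use Table 7.a for unscheduled, out-of-window and early-termination visits.
- Keep first-dose-based days for adverse events and exposure.
- State, with a cross-reference in SAP 7.9.3, that the Week 5 LOCF endpoint uses the last on-treatment observation irrespective of window, subject to the existing 7-day post-dose cut-off.

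The cost is a few sentences and one derivation, with no new data and no change to conduct. The drawback is that the windowing day will differ from treatment day for late starters, whose Week 5 score then reflects slightly less exposure.
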